## **2.7. Timing of Outcome and Covariate Assessments**

Participating households were followed from enrollment until the index child reaches (or would have reached, assuming a live birth and continued vitality) their first birthday. For the purposes of this analysis plan, severe pneumonia follow-up is through the first year of life.

HAP exposure was assessed prenatally and postnatally. The measurement periods were 24 hours. Prenatal exposures include one measurement at baseline (<20 weeks, denoted as the BL measurement in our trial) and two post-randomization (at 24-28 weeks' gestation denoted as P1; and at 32-36 weeks' gestation denoted as P2). We measured child postnatal exposures indirectly as a reconstructed average of maternal personal exposures and two area concentrations three times at ages 3 (denoted as the B1 measurement), 6 (denoted as B2) and at 12 months (denoted as B4). A validation subset of 10% of participants had double the numbers of measures, with extra measures at time points spaced between those of the main study.

Time-invariant covariates that are potential confounders and effect modifiers were collected at baseline and birth. If effects of time-varying exposures are considered, covariates that could be time-varying confounders were collected at quarterly household visits during infancy (e.g. vaccination, breast feeding).

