## **3.2. Analysis Populations**

The **exposure-response** analyses will include all follow-up time after birth and before death in study children whose households continue participating in HAPIN and who are at risk of a new severe pneumonia episode. No person-time is contributed to the cases of death of the mother prior to birth, miscarriage, stillbirth, and withdrawal from study prior to birth. Otherwise, person-time at risk was counted from the date of birth until the earliest date among the following: age 1 year, death of child, withdrawal from the study, or migration from the study area.

Missingness may affect exposure-response relationships. If the proportion missing exposure or confounder data is <10%, our study population for primary exposure-response analyses will be restricted to those

participants with complete data. If the proportion of exposure or confounder data missing is  $\geq 10\%$ , we will consider using multiple imputation methods to reduce missing data bias and loss of power.

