Mortality, n (%)	Binary	Death <30 days since diagnosis and/or Verbal Autopsy positive Yes/No

Children were permitted to meet the above case definition for severe pneumonia multiple times if the repeat event occurred either >14 days after the hospital discharge date or, if the hospital discharge data was not available or the child was not hospitalized, >30 days after the date the child met criteria for severe pneumonia. Implausible values and outliers identified from the variables that comprise the case definition will be considered missing. In addition to reporting the incidence rates of each endpoint, we will present the completeness of case ascertainment (e.g. proportion of reported healthcare visits with a screening, proportion of eligible cases with ultrasound assessment).

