As a secondary analysis we will conduct a time-to-event analysis using the Anderson-Gill method counting process method, which allows for repeated events for individuals. The start and stop times of the counting process will be defined according to the dates of exposure assessment for each child (i.e., birth to B1, B2 to B2, and B2 to B4), and the status will be classified as either pneumonia (where the outcome is 1) or no pneumonia (where the outcome is 0). Given that the underlying model based on Cox proportional hazards, we will test for proportionality of hazards assumption. To account for serial correlation of repeated time-to-event states for each child, we will use a sandwich estimator or random effects as defined by Amorim and Cai. The estimand for this model is a hazard ratio.

We will conduct subgroup analyses to identify potential effect modifiers: International Research Center (i.e., site), and known risk factors for severe infant pneumonia in LMICs (Table 5):

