## 6.2. Analysis Replication Plan

Selected components of the exposure-response analyses will be replicated by a second analyst. Secondary analyses of any outcome related to sensitivity analyses (i.e., alternative health model specifications, alternative covariate specification) will not be replicated.

The replication team will receive the following from the Data Management Core (DMC).

1. A cleaned analytic dataset. The dataset will also include baseline variables, covariates for subgroup analysis and covariates to include in the exposure-response analyses.
2. A table summarizing baseline characteristics (overall and by IRC).
3. The set of outcomes (primary and secondary).
4. For the exposure-response analysis only, the list of pre-specified covariates to be included in the regression models and forms of the exposure-response function.

Specific replication tasks include:

1. Replicate summary statistics (e.g., mean, standard deviation, percentages, proportion missing) in the baseline characteristic table.
2. Replicate exposure-response analyses for primary and secondary outcomes according to modelling strategies specified in Section 6.1.

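### The interval definition for the secondary Andersen-Gill model contains a zero-length row, omits B1–B2, and does not say that rows end at an episode or at study exit (minor)

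*SAP*

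**What the plan says.** Section 6.1 names a secondary time-to-event analysis by the Andersen-Gill counting process, chosen as a method "which allows for repeated events for individuals". On the rows it states: "The start and stop times of the counting process will be defined according to the dates of exposure assessment for each child". It then lists three intervals, introduced by i.e., and gives each row a status of 1 or 0: "dates of exposure assessment for each child (i.e., birth to B1, B2 to B2, and B2 to B4), and the status will be classified". The same paragraph plans a test of proportional hazards.

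Other parts of the SAP bear on these rows:

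- Section 2.7 places the postnatal assessments "three times at ages 3 (denoted as the B1 measurement), 6 (denoted as B2) and at 12 months (denoted as B4"). Table 4 changes the postnatal exposure value at the same ages.
- Section 3.2 limits person-time to children "who are at risk of a new severe pneumonia episode". It closes follow-up at the first birthday, death, withdrawal or out-migration, whichever comes first.
- Section 5.4 says that person-time may be treated as continuous, as weekly periods, or as broken up for moves and recent illness. It chooses none of these.
- Section 5.4, after Table 3, allows repeats: "Children were permitted to meet the above case definition for severe pneumonia multiple times if the repeat event occurred" more than 14 days after discharge or, without a discharge date, more than 30 days after the criteria were met.

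**The concern.** There are two faults of different kinds. The first is a printing error in an operative definition: one listed interval is empty and one that is needed is absent. The second survives the correction. If assessment dates are the only stop times, no row ends when an episode occurs. The episode is then dated at the next visit, the weeks after it stay in the risk set, and two episodes between the same two visits count as one. A child who dies or leaves between visits has no assessment date to close the row, and Table 2 counts some deaths as cases through verbal autopsy.

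Two analysts could therefore build different datasets from the same text, one following Section 6.1 alone and one adding Sections 3.2 and 5.4. What is at stake is event timing in a secondary model, and with it the planned proportional-hazards test.

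**Working it through.** **Inputs from the SAP.** 175 episodes in 2984 infants (Section 5.1); visits at 3, 6 and 12 months (Section 2.7); about 12,000 infant-quarters (Section 6.1). The SAP's own figures reproduce: 175/2984 = 5.9%, printed as 6%, and 2984 × 4 = 11,936.

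**Assumptions, not in the SAP.** Episodes evenly spread over the year unless stated; 30 days off risk after each episode; the effect patterns, frailty, exposure correlation and visit-date scatter used in the simulations.

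**1. Rows as printed.** 3 + 0 + 6 = 9 of 12 months. If 25% of episodes fall between 3 and 6 months, 0.25 × 175 ≈ 44 would have no row, and the standard error would grow by a factor √(1/0.75) = 1.155. For shares of 15% to 35% the loss is 26 to 61 episodes and the factor 1.08 to 1.24. With B1–B2 restored, the rows cover all 12 months and this loss disappears. The remaining steps assume that correction.

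**2. Delay in dating under visit-date coding.** The mean wait to the next visit is half the row length: 0.25 × 1.5 + 0.25 × 1.5 + 0.5 × 3 = 2.25 months. About 0.5 × 175 ≈ 88 episodes would be dated near 12 months. If 30% to 60% of episodes fall in months 6–12, the delay is 1.95 to 2.4 months and the count about 53 to 105.

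**3. Time after an episode left in the risk set.** 175 × 30/365.25 = 14.4 child-years, and 14.4/2984 = 0.5%.

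**4. Merged repeats.** Simulated with a 30-day gap and gamma frailty variance from 0 to 5, the three rows merge 1.2 to 6.4 of 175 episodes. Infant-quarters, the unit of the primary analysis, merge 0.6 to 3.2. The excess over the primary analysis is 0.6 to 3.2.

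**5. Hazard ratio.** Episode dates against visit dates gave 1.284 against 1.281 (SE 0.077 each). A separate repeat gave 1.278 against 1.275 (SE 0.077 each). A third layout, with a true value of 1.30 and the 30 days removed after each episode, gave 1.303 against 1.299 (SE 0.076 each). On the log scale the differences are 0.002 to 0.003, or 3% to 4% of one standard error.

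**6. Proportional-hazards check.** Percentage of runs rejecting at 5%, with 1000 runs per pattern (Monte Carlo SE at most 1.6 points), a residual-based test against age, between-visit exposure correlation 0.6, visit-date SD 0.35 month, and Table 4 cumulative means as exposure:

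| Assumed effect pattern | Episode dates | Visit dates |
|---|---|---|
| Constant | 4.3 | 4.7 |
| Linear decline to zero | 45 | 40 |
| Exponential waning | 50 | 46 |
| Stops at 6 months | 82 | 86 |
| Stops at 9 months | 49 | 30 |
| Months 6–9 only | 18 | 49 |

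A separate repeat gave 41 against 37 for the linear decline, 50 against 30 for the effect stopping at 9 months, and 16 against 39 for the effect in months 6–9 only. The false-rejection rate is sound under either coding. Under non-proportionality the visit dates may raise or lower rejection. In the last row they move an effect at 6–9 months to about 12 months.

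**The case against.** The best defence is that the SAP, read as a whole, already supports the right coding. Section 6.1 does not say that assessment dates are the only stop times. The method it names exists for repeat events, and an experienced analyst would split rows at them. Section 3.2 applies to the exposure-response analyses in general and supplies the closing dates, while Section 5.4 shows that the authors had thought of interruptions after an episode. Much of this stands. It reduces the second fault to a missing link between sections. It does not remove it, because Section 5.4 only lists options and nothing in Section 6.1 refers back.

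Three stronger readings are tempting and are not supported.

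- A reader might infer that a quarter of follow-up will be discarded. The schedule in Section 2.7 and the exposure windows in Table 4 leave B1–B2 as the only sensible middle interval, so the loss in step 1 describes the printed text and not a likely analysis.
- A reader might infer that Section 3.2 flatly contradicts Section 6.1. It sets an at-risk rule but prescribes no row break. The break is an inference from that rule together with the repeat-episode rule.
- A reader might infer that a miscoded dataset would escape the second analyst because of Section 6.2: "Secondary analyses of any outcome related to sensitivity analyses (i.e., alternative health model specifications, alternative covariate specification) will not be replicated". The same section also asks for replication of the primary and secondary outcomes under the strategies of Section 6.1, where this model sits, and Section 6.1 calls it a secondary analysis. The exemption cannot be assumed to apply.

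It is also fair to say that the proportional-hazards results rest on invented effect shapes, and that child age is already a planned effect modifier in Table 5.

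**Conclusion.** The definition is wrong as written, but the fault is minor and confined to a secondary analysis. The zero-length row is certain, and its correction is evident from the SAP itself. The missing rule for ending rows at episodes and exits is a small specification gap that matters only if Section 6.1 is followed to the letter. In that case the hazard ratio is essentially unchanged, about 0.5% of child-time is wrongly kept, and a few repeats merge. Episodes are dated about two months late on average if they are spread evenly.

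The planned proportional-hazards check is the one part that could be visibly affected. The direction and size depend on how the true effect varies with age, so no general loss of power can be claimed. The primary log-binomial analysis does not use these rows.

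**What to change.** In Section 6.1, print the intervals as birth–B1, B1–B2 and B2–B4, and add three statements:

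1. Assessment dates are the points at which the exposure value changes.
2. A row also ends at each episode date, with status 1, and at whichever closing date in Section 3.2 comes first.
3. After an episode the child re-enters when again at risk under the repeat-episode rule in Section 5.4.

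The cost is a few sentences and a change to the data step. The episode, discharge and exit dates are already needed for Sections 3.2 and 5.4, so no new data are required and the primary analysis stays as it is.

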**Table 5. Subgroup analysis (effect modifiers)**

Variables	Type	Definition/Assessment Methods
International Research Center	Categorical	Guatemala, India, Peru, Rwanda
Child age	Continuous	
Up-to-date vaccination status	Fixed and time-varying categorical	Receipt of 3 respiratory vaccines by one year of life, including 3 doses of pneumococcal conjugate vaccine, 3 doses of Haemophilus influenzae vaccine, one dose of measles vaccine (yes/no/missing)
COVID-19 pandemic	Categorical	Before and after March 15, 2020

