## 6. DATA ANALYSIS

### 6.1 Model specification

Our main aim is to estimate the exposure-response relationship between prenatal and postnatal HAP exposures and severe pneumonia incidence during the first year of life. The unit of observation in this analysis is infant-quarter. Occurrence of HAPIN severe pneumonia is the primary endpoint.

We will use log-binomial regression to estimate a risk ratio for the association between  $PM_{2.5}$  exposure and severe infant pneumonia on any given quarter. Exposure-response relationships will be modelled as follows:

$$\log E(y_{ij}) = \beta_0 + f(X_{ij}) + \sum_{k=1}^m \gamma_k \times Z_{ij}$$

where  $y_{ij}$  is the presence or absence of a severe pneumonia episode for the  $i^{th}$  infant and in the  $j^{th}$  quarter. The function  $f(X_{ij})$  represents a range of functions to capture the relationship between HAPIN severe infant pneumonia rates and HAP exposures. We will consider different types of functions for  $f(X_{ij})$ , including linear and polynomials including regression splines, and functional smooths using generalized additive models (GAMs). We will conduct visual assessment of observed versus predicted values to assess goodness-of-fit and use metrics like the Akaike Information Criteria or Root Mean Squared Error to compare models. The  $Z_{ij}$  represent the  $m$  potential confounders (Section 5.2) some of which are fixed ( $Z_i$ ) and others time-dependent ( $Z_{ij}$ ). We will either use generalized estimating equations (GEE) with a compound symmetry matrix and a robust variance estimator to account for serial correlation by child or generalized linear mixed models with random effects to account for heterogeneity among children.

We will consider different functional forms for  $f(X_{ij})$  to model pollutant exposures ( $PM_{2.5}$  and CO) separately for prenatal and post-natal exposures, i.e.,  $f_{prenatal}(X_{ij}) + f_{post-natal}(X_{ij})$ . For prenatal exposures, we will use the mean of the mother's three pre-natal measurements (at baseline, at 24-28 weeks, and 32-36 weeks). Not all mothers had all three measurements, although most did. We will use all available measurements to calculate a mean. It is possible that the effect of pre-natal exposures wanes over time. We will compare goodness-of-fit between models that consider the average (power value of 0) and those at different power values (a decay at a power value of 1, 2 or 3).

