**Table 4. Values of PM2.5 to use for exposure-response modeling.**

$t_{ij}$	Values for $X_{ij}$ (prenatal)*	Values for $X_{ij}$ (post-natal)
$t_{ij} \leq 3$		$X = \{PM_{2.5}(t = B1)\}$
$3 < t_{ij} \leq 6$		$X = \{PM_{2.5}(t = B1), PM_{2.5}(t = B2)\}$
$6 < t_{ij} \leq 12$	$X = \{PM_{2.5}(t = BL), PM_{2.5}(t = P1), PM_{2.5}(t = P2)\}$	$X = \{PM_{2.5}(t = B1), PM_{2.5}(t = B2), PM_{2.5}(t = B4)\}$

The error term for our regression model is a binomial distribution, and the canonical link is the logarithm function. Exponentiation of the difference between  $f(X_{ij})$  at different exposure values provides the risk ratio associated with that change in exposure. If we identify estimation problems when using the logarithm function, we will revert to use a logit function where exponentiation at different exposure values provides an odds ratio associated with that change in exposure. Since there are few cases (175 severe pneumonias) compared to the overall number of infant-quarters (~12,000), the odds ratio of a logistic regression should approximate the relative risk relatively well. We also do not expect zero-inflation to be a problem when using log or logit canonical links. The same log-linear (or logit) regression models will be used when using CO as the exposure, and in subgroup analyses and secondary outcomes, unless otherwise indicated.

*A priori* time-independent confounders will be crowding (number sleeping in house), IRC, SES, infant's sex and birthweight (or a z-score for birthweight for gestational age of child instead of birthweight). An SES score will be measured using a SES wealth index, but may also incorporate mother's education and nutrition data, and has been developed by our group and used in previous publications. *A priori* time-dependent confounders for the  $j^{\text{th}}$  quarter include age and season (winter or no), vaccination status, breastfeeding, and an indicator for pre vs post COVID-19 pandemic (i.e., 1 after March 15, 2020, and 0 otherwise).

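### Table 5 defines vaccination status only as completion by age one: as a fixed modifier this looks ahead, and as a time-varying one it overlaps with child age

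*SAP*

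**What the plan says.** Table 5 of the SAP types the vaccination modifier as "Fixed and time-varying categorical". The only definition in that row is "Receipt of 3 respiratory vaccines by one year of life". It is spelled out as three pneumococcal conjugate doses, three *Haemophilus influenzae* doses and "one dose of measles vaccine (yes/no/missing").

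Section 6.1 sets the model in which the modifier is used: "The unit of observation in this analysis is infant-quarter". The same regression form applies "in subgroup analyses and secondary outcomes, unless otherwise indicated".

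Vaccination also appears as a covariate. Section 6.1 (below Table 4) lists "age and season (winter or no), vaccination status, breastfeeding" among the time-dependent confounders for a given quarter, without defining vaccination status there. Section 2.7 says that covariates which could be time-varying confounders "were collected at quarterly household visits during infancy (e.g. vaccination, breast feeding").

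On follow-up, Section 3.2 states that "person-time at risk was counted from the date of birth until the earliest date among the following: age 1 year, death of child", withdrawal or migration. Table 2 counts deaths attributed to pneumonia by verbal autopsy as severe pneumonia.

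**The concern.** A status that is settled only at the end of the year is attached to records from earlier in the year. In the fixed version, a first-quarter episode is grouped by doses that may be given up to nine months after that quarter ends. The outcome can also help to decide the group. A child who dies of pneumonia before the last dose is an event but can no longer complete the series, so that event can never fall in the complete stratum.

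The time-varying version is named but has no rule of its own. If the printed rule is applied quarter by quarter, no child is positive until the seventh dose, and an infant fully on schedule at a young age is coded as not up to date. That contradicts the variable's name. It also makes vaccination strata partly age strata, while child age is a separate row of Table 5.

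At stake is the interpretation of one of the four listed effect modifiers. A difference between strata could reflect survival, retention or age rather than vaccination.

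**Working it through.** **The SAP's own figures.** Section 5.1 gives 2984 infants and 175 HAPIN severe pneumonias. Section 6.1 gives about 12,000 infant-quarters.
- 2984 × 4 = 11,936, which agrees with about 12,000.
- 175 / 2984 = 5.9%, which agrees with the stated 6%.

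**Doses required.** 3 + 3 + 1 = 7. All seven are needed for a positive status.

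**Fixed version: how many records are classified by later information.** Status is settled at the last dose or, failing that, at age one. Up to three of a child's four quarters therefore end before it is settled: 3 × 2984 = 8,952, and 8,952 / 11,936 = 75%. This is an upper bound, because a child who finishes the series earlier has fewer such quarters.

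**Fixed version: illustration of distorted stratum risks.** The SAP does not give the following inputs; they are assumptions.
- Share *v* of children who would complete by age one: 60% to 90%.
- Share *s* of cases among would-be completers who die or exit before the last dose and are coded no: 2% to 10%.
- No true association between vaccination and pneumonia, so the true risk ratio is 1.00.
- Early exits among non-cases are ignored.

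Formulas:
- Events moved from yes to no: *m* = 175 × *v* × *s*
- Risk in yes: (175*v* − *m*) / (2984*v* − *m*)
- Risk in no: (175(1 − *v*) + *m*) / (2984(1 − *v*) + *m*)

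Low end, *v* = 0.6 and *s* = 0.02:
- *m* = 2.1
- yes: 102.9 / 1788.3 = 0.0575
- no: 72.1 / 1195.7 = 0.0603
- apparent no-versus-yes ratio: 1.05

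High end, *v* = 0.9 and *s* = 0.10:
- *m* = 15.75
- yes: 141.75 / 2669.85 = 0.0531
- no: 33.25 / 314.15 = 0.1058
- apparent no-versus-yes ratio: 1.99

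| *v* | *s* = 0.02 | *s* = 0.05 | *s* = 0.10 |
|---|---|---|---|
| 0.60 | 1.05 | 1.12 | 1.26 |
| 0.75 | 1.08 | 1.20 | 1.41 |
| 0.90 | 1.19 | 1.48 | 1.99 |

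About 2 to 16 of the 175 events change stratum. If these children are coded missing instead, their events leave both strata. The table concerns stratum risks only and says nothing about the size of any bias in the PM2.5 interaction.

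**Time-varying version.** No arithmetic is possible, because the SAP gives no vaccination schedules. The reasoning is from the text: with seven doses required, every child starts at no and can turn positive only after the last dose. Positive quarters therefore always come after a child's negative ones. Table 4 also builds postnatal exposure from different measurements at different ages, so age-sorted strata would differ in how exposure is constructed as well.

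**The case against.** The strongest reply is that the plan already intends a time-varying version. The row says so, vaccination was recorded at quarterly visits, and Section 6.1 treats it as time-dependent. A status built from doses received to date uses no future information. This stands: the looking-ahead problem belongs to the fixed version alone. It does not remove the point, because the row keeps the fixed version, does not say which one defines the subgroup, and gives no rule by quarter or by age.

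The second reply concerns the estimand. Table 5 asks whether the PM2.5 risk ratio differs by vaccination status, not whether vaccinated children have less pneumonia. If the true PM2.5 risk ratio is the same in both strata, and early death or exit among cases is unrelated to exposure, moving cases between strata shifts their baseline risks but leaves the PM2.5 risk ratios essentially unchanged. This stands too. A reader might infer from the illustration that the interaction is biased by a similar amount; the SAP does not support that.

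A reader might also infer that the primary estimate is affected because vaccination is an a priori confounder. Section 6.1 does not tie that covariate to the Table 5 rule, and Section 5.2 refers to the study codebook for confounders, so the link is not established.

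Nor is it right that every child who dies or leaves early is barred from a positive status. One who has completed all seven doses beforehand meets the definition, and a missing category exists. Whether early leavers are analysed is itself unclear: Section 3.2 counts their time up to exit, while Section 4.1 restricts the analysis to households continuing through trial exit.

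Finally, age is already a covariate. That adjusts for its main effect but does not separate two effect modifiers that move together. How closely they move depends on schedules not given.

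**Conclusion.** The point holds for the Table 5 modifier. One rule, completion of seven doses by age one, is offered for two differently typed variables and suits neither in an infant-quarter model. As a fixed variable it classifies up to 75% of infant-quarters by later information, and it shuts pneumonia deaths that occur before the last dose out of the complete stratum. As a time-varying variable read literally, it codes on-schedule young infants as not up to date and overlaps with child age.

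The apparent stratum risk ratio of 1.05 to 1.99 against a true 1.00 rests wholly on assumed completion and exit shares. The SAP does not give the number of deaths or exits before completion. No bias in the PM2.5 interaction has been shown, and no effect on the primary estimate follows unless the confounder is coded by the same rule. This should be corrected before the subgroup analysis is run; it is not a fault that undermines the primary analysis.

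**What to change.** In Table 5 and Section 6.1:
- Do not use the fixed by-age-one status for effect modification.
- Define status at the start of each quarter: doses received to date compared with doses due at that age under the site's schedule.
- State how children who die or exit before completing the series are coded, including when missing applies.
- State that the time-dependent vaccination confounder uses the same definition.

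The cost is recoding. It needs each country's vaccination schedule and either dose dates or the quarterly-visit records. Section 2.7 shows that vaccination was collected quarterly, but the SAP does not show that individual dose dates exist. If they do not, status can be fixed only to the nearest visit, and the SAP should say so.
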